6.8 Compliance

Investigators are required to conduct the study in compliance with the protocol. Compliance with the protocol will be closely monitored. Important aspects of compliance with this clinical trial include:

- Eligibility,
- Tarloxotinib administration, including:
 - Dose calculation
 - Dose modification
 - Infusion duration
- Performance of protocol-specified assessments,

^{*} May hold or reduce if nausea/vomiting continues despite optimized anti-emetic treatment

^{**} Tarloxotinib-related toxicity meeting the definition of Hy's Law, tarloxotinib will be discontinued permanently

Confidential and Proprietary

- ECG monitoring, and
- AE reporting

Protocol deviations are defined as any departure from the protocol or associated instructions and will be monitored. Deviations from the protocol, including violations of inclusion/exclusion criteria, will be assessed as "minor" or "major." Protocol deviations at investigational sites will be discussed with the Investigator and additional training will be provided as needed to secure Investigator compliance.

Study staff will receive additional training as needed to prevent non-compliance.

6.9 Study Visits

Protocol-required assessments scheduled for each study visit are summarized in the Schedule of Events and described below. All assessments with a time point relative to study treatment infusion may be performed in the 5 minutes prior to and following the protocol-specified time. Any assessment that is not able to be collected at the protocol-specified time (e.g., blood sample for pharmacokinetic testing) should be obtained as soon as practicable and the actual date/time of collection recorded.

6.9.1 Screening Period/Baseline Assessments

Patients may be screened anytime during the 28 days prior to Cycle 1 Day 1. Unless otherwise specified, baseline assessments may be done anytime following consent and prior to the first study drug administration. Patients who are determined not to meet eligibility criteria at any time prior to Cycle 1, Day 1 will not receive study drug. The following will be assessed or measured at screening/baseline:

- Informed consent
- Eligibility (including tumor assessment)
- Medical/Disease history
- Smoking history: Smoking history should be documented in the eCRF page as "never", "former" (with quit date), or "current" (document pack years).
- Demographics
- Physical examination
- Weight
- ECOG
- Vital signs
- ECG (12-lead)
- Hematology panel
- Serum chemistry panel

Confidential and Proprietary

- Urinalysis
- Pregnancy test
 - Serum pregnancy test within 3 to 7 days of Cycle 1 Day 1
- Tumor tissue
 - FFPE block from newly obtained biopsy or archive tissue of at least 8 to 10 slides
 Note: Adequacy must be confirmed by local pathologist.
- Concomitant medications
 - o Record all concomitant medications use after 14 days prior to Cycle 1 Day 1
 - Special attention should be accorded to medications that are known to cause prolongation of QTc or deplete potassium
- Conduct baseline radiographic tumor assessment
 - O Perform according to institutional practice; include CT or MRI of the chest and abdomen, brain scan, and bone scan. The baseline radiographic tumor assessment is required within 28 days prior to the first dose of tarloxotinib. Brain and bone scans do not need to be repeated for patients with no brain or bone metastases at baseline. A recently completed negative positron emissions tomography (PET) scan can be substituted for the baseline bone scan.

6.9.2 Treatment Period

The following will be assessed or measured at the indicated study days:

Day 1

- Complete physical examination
- ECOG (Cycle 1)
- Weight
- Vital signs
 - o Pre-infusion
 - End of infusion (EOI)
 - \circ 30, 60, and 90 minutes after EOI (\pm 10 minutes)
- ECG (12-lead)
 - o Cycle 1
 - Pre-infusion
 - EOI
 - 1, 2, 3, and 4 hours after EOI (\pm 10 minutes)
 - Hourly thereafter as needed (see Section 6.9.2.1)
 - o Cycle 2
 - Pre-infusion

Confidential and Proprietary

Rain Therapeutics Inc.

- EOI
 1, 2, 3, and 4 hours after EOI (± 10 minutes)
- Hourly thereafter as needed (see Section 6.9.2.1)
- o Cycles 3+
 - Pre-infusion
 - 2 hours after EOI (± 10 minutes)
 - 4 hours after EOI (patients with QTcF \geq 501 msec) (\pm 10 minutes)
 - Hourly thereafter as needed (see Section 6.9.2.1)
- Hematology panel
- Serum chemistry panel
- Serum potassium (Cycles 1 and 2 only)
 - o EOI
 - o 3 hours after EOI (\pm 10 minutes)
- Urinalysis
- Pregnancy test
 - Urine (dipstick allowed)
- PK samples (Cycles 1 and 2 only)
 - o Pre-infusion (± 5 minutes)
 - \circ EOI (\pm 5 minutes)
 - o 3 hours after EOI (\pm 10 minutes)
 - o 7 hours after EOI (in a subset of patients on Cycle 1 Day 1 only) (\pm 10 minutes)
- Blood sample for biomarkers (e.g., ctDNA) (Cycles 1 and 2)
- Ensure that all electrolytes are within normal ranges
- Potassium supplementation, if applicable (See Table 5)
- Premedication, as applicable per local institutional guideline
- Tarloxotinib infusion (at least 1 hour in duration)
- Concomitant medications
- Assess AEs

Days 8, 15, and 22

- Vital signs
 - Pre-infusion
 - o EOI
 - \circ 30, 60, and 90 minutes after EOI (\pm 10 minutes)
- ECG (12-lead)

Confidential and Proprietary

- o Cycle 1
 - Pre-infusion
 - EOI
 - 1, 2, 3, and 4 hours after EOI (\pm 10 minutes)
 - Hourly thereafter as needed (see Section 6.9.2.1)
- o Cycles 2+
 - Pre-infusion
 - 2 hours after EOI (± 10 minutes)
 - 4 hours after EOI (patients with \geq Grade 3 QTcF prolongation) (\pm 10 minutes)
 - Hourly thereafter as needed (see Section 6.9.2.1)
- Serum chemistry panel
- Urinalysis (Cycle 1 only)
- Optional tumor biopsy
 - o Day 15 after EOI (preferred) or Day 16 (within 24 hours of any EOI)
 - Plasma samples for PK and biomarkers should be obtained as close to the time of biopsy as possible
- Ensure that all electrolytes are within normal ranges
- Potassium supplementation, if applicable (See Table 5)
- Premedication, as applicable per local institutional guideline
- Tarloxotinib infusion (at least 1 hour in duration)
- Concomitant medications
- Assess AEs

Note: Pre-infusion assessments scheduled for Day 1 of Cycles 2 and later cycles are considered Day 29 of the prior cycle. If any patient is not proceeding to an additional cycle, the assessments scheduled for the EOT should be performed within \pm 7 days of their last dose of tarloxotinib.

Every 8 weeks (± 5 days) From Cycle 1 Day 1

- Radiographic tumor assessments
 - The first post-baseline radiographic tumor assessment will occur 8 weeks after the Cycle 1 Day 1 visit. The same imaging modality used for baseline imaging (i.e., CT or MRI) must be used for subsequent radiographic tumor assessments.

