Adverse Events Assessment \leftarrow Every Visit \rightarrow \parallel X \parallel X	Adverse Events Assessment														X		X

Confidential and Proprietary

CT = computed tomography; ECOG = Eastern Cooperative Oncology Group; EOI = end of infusion; EOT = End-of-Treatment Visit; FUP = Follow-up Visit; MRI = magnetic resonance imaging; OBX = optional biopsy; PET = positron emissions tomography; PK = pharmacokinetic; QTcF = corrected QT interval as calculated according to Fridericia's formula; SCR = Screening Period

- * Patients will be asked about their previous smoking history (including cigarettes, cigars, pipes, and vaping devices).
- [†] For patients with Grade 3 QTcF prolongation (≥ 501 msec or > 60 msec increase compared to pre-infusion), repeat ECG every 15 to 30 minutes until resolved to Grade 2 (481 to 500 msec) or lower (≤480 msec) and then obtain ECGs every hour.
- ‡ Can be made ± 5 minutes (pre-infusion and EOT) and ± 10 minutes (3 hours and 7 hours) of scheduled event.
- 1 = For patients with \geq Grade 3 (\geq 501 msec) QTcF prolongation with current or prior infusion
- ² = Serum pregnancy at baseline, then urine dipstick, for women of childbearing potential
- 3 = In a subset of patients
- ⁴ = Collect blood (plasma samples for PK and biomarker including circulating tumor deoxyribonucleic acid) at time of biopsy
- 5 = If applicable (see Section 6.4)
- ⁶= Collect blood (plasma sample for biomarker) at time of biopsy
- ⁷ = Perform radiographic tumor assessments according to institutional practice; include CT or MRI of the chest and abdomen, brain scan, and bone scan at baseline. The baseline radiographic tumor assessment is required within 28 days prior to the first dose of tarloxotinib. A recently completed negative PET scan can be substituted for the baseline bone scan. The same imaging modality used for baseline imaging (i.e., CT or MRI) must be used for subsequent tumor assessments in each patient.

Note: Day 1 of Cycles 2+ is Day 29 of the prior cycle. The EOT Visit should be conducted within \pm 7 days of the last dose of tarloxotinib, and the safety FUP should occur 30 days (\pm 7 days) after the last dose of tarloxotinib.

TABLE OF CONTENTS

Do	cum	ent I	listory	2
Sta	item	ent o	f the Sponsor	9
Syı	nops	sis		10
Ta	ble o	of Co	ntents	18
Lis	t of	Tabl	es	21
Lis	t of	Figu	res	22
Lis	t of	Abb	reviations	23
1.]	Intro	ductionduction	25
2.]	Back	ground Information	25
2	2.1	Inv	estigational Product: Tarloxotinib	25
2	2.2	Stu	dy Diseases	26

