Pharmacokinetic (PK) samples were collected from patients after administration of the first dose in Cycles 1 and 2. No accumulation of tarloxotinib was observed on Cycle 2 Day 1 as compared to Cycle 1 Day 1 for any PK parameter. The data obtained across all dose levels were consistent with linear pharmacokinetics for both tarloxotinib and tarloxotinib-E. The mean elimination half-life of tarloxotinib was approximately 5 hours at the 150 mg/m² dose level, and mean C_{max} was 20.54 μ g/mL. Across the range of doses, plasma concentrations of tarloxotinib-E averaged about 1% of those of tarloxotinib.

Study TH-CR-601 and Study TH-CR-602

Two Phase 2, open-label studies were subsequently performed to evaluate tarloxotinib administered as a 150 mg/m² weekly 1-hour IV infusion in patients with EGFR-mutant, T790M-negative, advanced NSCLC that was resistant to EGFR TKIs (Study TH-CR-601), and in patients with recurrent or metastatic SCC of the head and neck or skin (Study TH-CR-602). These studies failed to show significant antitumor activity. It is believed that both trials enrolled a study population unlikely to respond to EGFR inhibition. Tumors lacking EGFR T790M as their EGFR TKI resistance mechanism are not likely to be EGFR dependent due to enrichment for tumors with bypass signaling or other non-EGFR-dependent signaling mechanisms; therefore, no EGFR inhibitor, including tarloxotinib, would be expected to show benefit in this population. Additionally, SCC is not known to be dependent on EGFR signaling. Data from these 2 studies are in the process of being analyzed and should be considered preliminary and subject to change.

Study TH-CR-601 enrolled 21 subjects. A total of 223 AEs related to tarloxotinib were reported in 21 subjects during the study. Of these, 17 subjects (81%) experienced Grade 3 AEs, and 1 subject (5%) experienced a Grade 4 AE. QTc prolongation accounted for most of the Grade 3 toxicities (10 subjects, 48%). This was mainly due to corrected QTc interval as calculated according to Fridericia's formula (QTcF) change from baseline of > 60 msec (38%) while 2 subjects (10%) developed QTcF \ge 501 msec. None were associated with clinically significant arrhythmia. Other Grade 3 toxicities included hypertension in 2 subjects and various other events in 1 subject each. Grade 4 events related to tarloxotinib included 1 event of cerebrovascular accident, while no one experienced Grade 5 toxicity.

Confidential and Proprietary

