Grade 2 481 to 500 msec QTcF	 Continue the same tarloxotinib dose for subsequent cycles Cycle 1 and Cycle 2 Day 1 May be discharged if the 4-hour (or later) post-infusion QTcF is ≤ Grade 2 and the patient is asymptomatic After Cycle 2 Day 1 Obtain pre-infusion and 2-hour post-infusions ECGs May be discharged if the 2-hour or later post-infusion QTcF is ≤ Grade 2 and the patient is asymptomatic Continue the same tarloxotinib dose for subsequent cycles 		
Grade 3 ≥ 501 msec QTcF	 Obtain ECGs every 15 to 30 minutes until QTcF is ≤ Grade 2 and then obtain ECGs every 1 hour May be discharged home if 2 subsequent measurements (at least 15 minutes apart) after the 4-hour post-infusion QTcF is ≤ Grade 2 and no significant arrhythmias If QTcF is ≥ 601 msec, permanently discontinue tarloxotinib If QTcF ≥ 501 msec and ≤ 600 msec Resume tarloxotinib dosing with dose reduction 1st occurrence: reduce to 100 mg/m² 2nd occurrence: reduce to 75 mg/m² 3rd occurrence: permanently discontinue tarloxotinib Obtain ECGs prior to and hourly (for at least 4 hours) following the next tarloxotinib infusion 		
Grade 3 > 60 msec increase from pre-infusion QTcF AND ≤ 500 msec QTcF	 Obtain ECGs every 15-30 minutes until QTcF is ≤ Grade 2 and then obtain ECGs every 1 hour May be discharged home if 2 subsequent measurements (at least 15 minutes apart) after the 4-hour post-infusion QTcF is ≤ Grade 2 and no significant arrhythmias Obtain ECGs prior to and hourly (for at least 4 hours) following the next tarloxotinib infusion 		
Grade 4 TdP or polymorphic ventricular tachycardia, signs/symptoms of serious arrhythmia	Place patient on telemetry and obtain ECGs as clinical indicated Obtain Cardiologist consult and admit to hospital for extended observation on telemetry Permanently discontinue tarloxotinib		

ECG = electrocardiogram; msec = millisecond; QTcF = corrected QT interval as calculated according to Fridericia's formula; TdP = Torsade de Pointes

Note: If QTcF prolongation is ≥ Grade 3, an ECG may need to be repeated more frequently during the patient's

Confidential and Proprietary

visit depending on the degree of the prolongation and per institutional standards.

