6.9.2.1 Electrocardiogram Guidance for QT Prolongation During the Treatment Period

In the event of QTcF prolongation (\geq 501 msec or > 60 msec increase compared to pre-infusion), repeat ECG every 15 to 30 minutes until resolved to Grade 2 (481 to 500 msec) or lower (\leq 480 msec) and then obtain ECGs every hour. For patients who have had a Grade 3 event of

Confidential and Proprietary

QTcF prolongation at a previous infusion ECGs should be conducted hourly for the 4 hours following the subsequent infusion.

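### The protocol gives conflicting triggers for extended ECGs after Grade 3 QTcF prolongation: the Day 1 list for Cycles 3+ uses QTcF of 501 msec or more only, while Table 7 and Section 6.9.2.1 also count a rise above 60 msec

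*Protocol*

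**What the plan says.** The protocol defines Grade 3 QTcF prolongation in Sections 6.7.1, 6.9.2.1 and 8.5 as an absolute QTcF of 501 msec or more, or a rise of more than 60 msec from the pre-infusion value. Follow-up ECGs after such an event are then set in several places.

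**Absolute limit only**
- Section 6.9.2, Day 1, Cycles 3+: "4 hours after EOI (patients with QTcF \geq 501 msec".
- Schedule of Events, footnote 1: "For patients with \geq Grade 3 (\geq 501 msec) QTcF prolongation with current or prior infusion".

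**Any Grade 3 event**
- Section 6.9.2, Days 8, 15 and 22, Cycles 2+: "4 hours after EOI (patients with \geq Grade 3 QTcF prolongation".
- Section 6.9.2.1, for patients with an earlier Grade 3 event: "QTcF prolongation at a previous infusion ECGs should be conducted hourly for the 4 hours" after the next infusion.
- Section 6.7.1, Table 7. Both Grade 3 rows, including the separate row for a rise above 60 msec with QTcF at 500 msec or below, say: "Obtain ECGs prior to and hourly (for at least 4 hours) following the next tarloxotinib infusion".

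The Day 1 list for Cycles 3+ also carries, directly below the restricted line, "Hourly thereafter as needed (see Section 6.9.2.1".

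**The concern.** The Day 1 list and Table 7 cannot both be followed as written for a patient whose Grade 3 event was a rise above 60 msec without reaching 501 msec. One asks for hourly ECGs to 4 hours at the next infusion. The other offers the 4-hour ECG only to patients at or above the absolute limit.

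The protocol calls QT prolongation the main identified risk of the drug (Section 2.5) and reports prolongation up to 4 hours after the end of infusion (Section 2.6). After Cycle 2 Day 1, the Grade 1 and Grade 2 rows of Table 7 allow an asymptomatic patient to leave after the 2-hour ECG. A site that works strictly from the Day 1 list could therefore omit readings that Table 7 and Section 6.9.2.1 require.

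There is also a smaller cost to the analysis. SAP Section 14.4 summarises QTcF at each scheduled ECG time point. If sites followed different pages, the patients contributing 4-hour values in later cycles were not selected by one rule.

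**Working it through.** **1. The rules applied to one patient.** Take a patient with a rise above 60 msec and QTcF at 500 msec or below on Day 22 of Cycle 2 or later, who then attends Day 1 of the next cycle.

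| Source | ECGs required on that Day 1 |
|---|---|
| Section 6.9.2, Day 1, Cycles 3+ | pre-infusion and 2 hours; the 4-hour line does not apply |
| Section 6.9.2.1 | hourly for 4 hours |
| Table 7, change-only row | pre-infusion, then hourly for at least 4 hours |

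The Day 1 list gives 2 ECGs. Table 7 gives at least 1 + 4 = 5. The difference is at least 3 ECGs, at 1, 3 and 4 hours. Every change-only patient falls outside a trigger of 501 msec or more, by definition.

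**2. Where the narrow wording applies.** Section 6.9.2 schedules the 4-hour ECG for everyone on all four infusion days of Cycle 1 and on Cycle 2 Day 1. Days 8, 15 and 22 of Cycles 2+ use the Grade 3 trigger. That leaves Day 1 of Cycles 3+. Section 11.3 expects up to 10 cycles, so the count is at most 8 visits out of 10 × 4 = 40 infusions (20%). With a look-back to the next infusion only, the conflict needs a change-only event at the infusion just before one of those 8 visits.

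**3. How common change-only events were before (context only).** Protocol Section 2.3.2 gives these inputs.

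*TH-CR-601.* There were 21 patients, 10 of them with Grade 3 QTc prolongation (48%). The split is reported as "change from baseline of > 60 msec (38%) while 2 subjects (10%) developed QTcF" of 501 msec or more.
- 10/21 = 47.6%, 8/21 = 38.1% and 2/21 = 9.5%, matching the stated 48%, 38% and 10%.
- 8 + 2 = 10, so the split accounts for all Grade 3 patients. Change accounts for 8/10 = 80%.

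*Both Phase 2 studies.* Ten patients (21%) reached 501 msec or more and 16 (34%) had a change above 60 msec. Both percentages round correctly only with a denominator of 47 (10/47 = 21.3%, 16/47 = 34.0%), although 51 patients were enrolled. The overlap is not given, so the change-only share of patients meeting either criterion can only be bounded:
- full overlap: 16 patients meet either criterion, and 16 − 10 = 6 are change-only, so 6/16 = 38%;
- no overlap: 26 meet either criterion and 16 are change-only, so 16/26 = 62%;
- if the 19 patients reported with Grade 3 events are exactly those meeting either criterion: overlap = 10 + 16 − 19 = 7, change-only = 16 − 7 = 9, so 9/19 = 47%.

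**The case against.** The strongest reply is that the Day 1 list already leads to the wider rule. The line below the restricted one sends the site to Section 6.9.2.1, which gives the full Grade 3 definition and the hourly ECGs at the next infusion. This has force: the wider rule can be reached from the list, so it would be wrong to say that the list rules out further ECGs. But the line concerns ECGs after the 4-hour point and is conditional on need. It does not lift the explicit restriction above it or say which text governs.

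The Schedule of Events is weaker evidence than it may look. Its dagger footnote includes the rise above 60 msec, though for an event at the current infusion. The available text of the table is damaged, so the rows that footnote 1 governs cannot be confirmed. The SAP's copy of the schedule marks a 4-hour ECG at every treatment visit, and SAP Section 6.3.2.4 lists it after Cycle 1 without a trigger. A reader might infer that the Schedule itself removes the 4-hour ECG; that is not established. The conflict rests on Section 6.9.2 set against Section 6.9.2.1 and Table 7.

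Two further readings are tempting:
- That most patients with a Grade 3 event would lose enhanced monitoring. A change-only majority is shown only in TH-CR-601; the pooled bounds of 38% to 62% include values below one half.
- That 48% against 10%, a gap of about 38 points, measures the defect. Those are rates at any time in an earlier study, not rates at the infusion before Day 1 of Cycle 3 or later.

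It also stands that the 2-hour ECG is required for everyone under either rule. Section 2.3.2 puts the mean maximum change at 2 to 3 hours after the end of infusion, so the narrow list does not miss that whole period. The look-back differences are partly verbal: next and subsequent infusion mean the same, while footnote 1 adds the current infusion and the visit lists give none.

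**Conclusion.** The point holds as an internal contradiction in the current protocol text. A patient with a change-only Grade 3 event at the infusion before Day 1 of Cycle 3 or later is covered by Table 7 and Section 6.9.2.1 but excluded from the 4-hour line of the Day 1 list, and nothing says which rule governs. A site following that list exactly would omit at least three ECGs that the other passages require at that visit.

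The reach is limited to at most 8 of 40 infusions over 10 cycles, and only after such an event at the preceding infusion. That count assumes no missed doses and a look-back of one infusion. The documents give no rate for this situation, so the number of patients affected cannot be stated. The TH-CR-601 split shows that change-only events are not rare, and supports no more than that. Whether the absolute limit alone or either criterion should be the trigger is a clinical matter on which this point takes no position.

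**What to change.** Reconcile the two ECG lists in Section 6.9.2 (Day 1 of Cycles 3+, and Days 8, 15 and 22 of Cycles 2+), Schedule of Events footnote 1, Section 6.9.2.1 and Table 7. State one trigger (the absolute limit alone, or the absolute limit or the rise) and one look-back in a single place, and have the visit lists and the footnote refer to it. The sponsor's clinical team must decide which reading applies.

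The cost is protocol wording. If the wider reading is chosen, add about three ECGs at each affected visit, in patients already flagged as Grade 3.

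The SAP records that the study was discontinued early and the database locked with 41 patients enrolled. Rewording cannot change those data. For them, the study report should say which rule sites followed for the 4-hour ECG in later cycles.

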6.9.2.1 Electrocardiogram Guidance for QT Prolongation During the Treatment Period

In the event of QTcF prolongation (\geq 501 msec or > 60 msec increase compared to pre-infusion), repeat ECG every 15 to 30 minutes until resolved to Grade 2 (481 to 500 msec) or lower (\leq 480 msec) and then obtain ECGs every hour. For patients who have had a Grade 3 event of

Confidential and Proprietary

QTcF prolongation at a previous infusion ECGs should be conducted hourly for the 4 hours following the subsequent infusion.

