- All patients are under direct supervision of qualified personnel with immediate availability of appropriate resuscitation equipment. Patients will therefore be under intense monitoring and supervision during the entire period they are at risk for QT prolongation.
- Patients will not be discharged unless they have ≤ Grade 2 QTcF.

In the prior Phase 1 and 2 Phase 2 studies, the main identified risk of tarloxotinib treatment (QT prolongation) was observed primarily within a 3- to 4-hour period following the start of infusion.

Confidential and Proprietary

Given the absence of effective treatment options for NSCLC patients with EGFR exon 20 insertion or HER2-activating mutations and based upon the manageability of observed risks associated with tarloxotinib, the risk-to-benefit ratio for participants in this study is acceptable. This risk of QT prolongation is mitigated in this study by the medical supervision of patients during first 3 to 4 hours of drug administration, when the risk of an event is greatest, with additional guidance on management of QT prolongation provided in the protocol and the Tarloxotinib Investigator's Brochure.

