6.7.1 Treatment Guidelines for QTc Prolongation

Immediate medical management of patients will be based on the following:

- 1. Baseline: A pre-infusion (baseline) ECG will be obtained on all patients, if the automated measurements indicate a QTcF of \geq 450 msec
 - a. The single QTcF will be verified by manually measuring at least 3 complexes within the ECG and determining the average QTcF
 - b. All patients must have a pre-infusion QTcF of < 450 msec by either:
 - i. Calculation using the automated measurements of the first ECG or
 - ii. The manual measurement of a single ECG

If it is determined that the manually read QTcF \geq 450 msec, the Medical Monitor should be contacted to discuss the clinical significance of the reading and to determine if it is appropriate to move forward with the infusion.

2. During treatment: Grade 3 QTc prolongation (any QTcF that is ≥ 501 msec OR > 60 msec QTcF increase relative to pre-infusion) will be manually verified by measuring at least 3 complexes with the ECG and determining the average QTcF. If QTcF prolongation is ≥ Grade 3, an ECG may need to be repeated more frequently during a patient's visit, depending on the degree of the prolongation, as indicated in Table 7 and per institutional standards.

Note: Dose modification will be based on the average QTcF using the manual measurements.

Confidential and Proprietary

If the Investigator has any question regarding the local automated reading, a local cardiologist should be consulted. Treatment guidelines for patients experiencing QTc prolongations are provided in (Table 7).

Patients who experience \geq Grade 3 QTc prolongation must be assessed by the Investigator (or qualified designee) prior to discharge.

Table 7: Treatment Guidelines for QTc Prolongation

QTc Prolongation	After Tarloxotinib Administration		
Grade 1 450 to 480 msec QTcF	 Cycle 1 and Cycle 2 Day 1 May be discharged if the 4-hour (or later) post-infusion QTcF is Grade 1 or lower and asymptomatic After Cycle 2 Day 1 Obtain pre-infusion and 2-hour post-infusion ECGs May be discharged if the 2-hour (or later) post-infusion QTcF is ≤ Grade 1 and the patient is asymptomatic 		

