8.5 Reporting QTc Prolongation

QT prolongation is not unexpected but it is an AE of special interest (AESI). Grade 3 AESIs require expedited reporting to the Sponsor. ECGs will be obtained throughout the study and will be read locally at the investigational sites. Grade 3 QTc prolongation (absolute QTcF of \geq 501 msec or QTcF increase of > 60 msec relative to pre-infusion) or Grade 4 QTc prolongation will be reported as an AESI.

Any apparent Grade 3 AESIs should be verified by manually measuring at least 3 complexes within the ECG and determining the average QTcF.

AESIs will be reported by submitting an AESI Report to:

[contact]

All events of Grade 3 QTc prolongation (absolute QTcF of \geq 501 msec or QTcF increase of \geq 60 msec relative to pre-infusion) or Grade 4 QTc prolongation will be reported as an AESI unless the event met the criteria of serious (see Section 8.1.1.4) in which case it will be reported as an SAE.

Confidential and Proprietary

Table 12: NCI CTCAE Grading of ECG QTc Prolongation (Medical Dictionary of Regulatory Activities Code: 10014383)

ECG QTc Prolongation NCI CTCAE Grade					
1	2	3	4	5	
Average QTc	Average QTc	Average	Torsade de Pointes	Not applicable	
450 to 480 msec	481 to 500 msec	$QTc \ge 501 \text{ msec}$	OR		
		OR	polymorphic		
		> 60 msec change	ventricular		
		from baseline*	tachycardia		
			OR		
			signs/symptoms of		
			serious arrhythmia		

Adapted from NCI CTCAE v5.0

ECG = electrocardiogram; NCI CTCAE = National Cancer Institute Common Terminology Criteria for Adverse Events; QTc = corrected QT interval; QTcF = corrected QTc interval as calculated according to Fridericia's formula

Definition of QTc prolongation: A finding of a cardiac dysrhythmia characterized by an abnormally long QTc * Although a Grade 3 event (≥ 501 msec OR > 60 msec change from baseline) is reportable as an adverse event of special interest, dose reductions are not required for patients with absolute QTcF ≤ 500 msec and a ≤ 60 msec QTcF change from baseline.

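### The rule that ends 15 to 30 minute ECGs ignores the change limb of Grade 3, so for a rise above 60 msec with QTcF at or below 500 msec it is met at the triggering ECG

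*Protocol*

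**What the plan says.** **Trigger.** Protocol Section 6.9.2.1 starts repeat ECGs for QTcF of at least 501 msec or a "> 60 msec increase compared to pre-infusion". Section 6.7.1 defines Grade 3 during treatment as QTcF of at least 501 msec "OR > 60 msec QTcF increase relative to pre-infusion". Section 8.5 uses the same two limbs for adverse events of special interest ("QTcF increase of > 60 msec relative to pre-infusion").

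**Stop rule.** Section 6.9.2.1 tells sites to "repeat ECG every 15 to 30 minutes until resolved to Grade 2 (481 to 500 msec) or lower", and glosses lower as 480 msec or less. The Schedule of Events footnote has the same end point: "until resolved to Grade 2 (481 to 500 msec) or lower (≤480 msec) and then obtain ECGs every hour". Neither mentions the change from pre-infusion.

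**Table 7 (Section 6.7.1).** Grade 3 by change alone has its own row, headed "> 60 msec increase from pre-infusion QTcF AND ≤ 500 msec QTcF". That row orders ECGs every 15 to 30 minutes and ends them at Grade 2 or lower, with no msec value. On discharge it says "May be discharged home if 2 subsequent measurements (at least 15 minutes apart) after the 4-hour post-infusion QTcF is ≤ Grade 2", and it adds that there must be no significant arrhythmia. Section 6.7.1 also requires assessment by the investigator or a qualified designee before a Grade 3 patient leaves.

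**Section 2.5** lists as a safeguard: "Patients will not be discharged unless they have ≤ Grade 2 QTcF".

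**Text after Table 7.** Treatment and retreatment guidance is said to rest on absolute QTcF and to differ from the CTCAE. The explanation and the example that follow are about dose reduction.

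**The concern.** A rule that starts on either of two conditions should say what happens to both when it ends. Here one limb drops out. For patients in the change-based row of Table 7, one section orders close monitoring and another ends it before the first repeat ECG.

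The protocol treats QT prolongation as the main identified risk. In the two earlier Phase 2 studies the mean maximum QTcF change was 51 msec at 3 hours and 55 msec at 2 hours after the end of infusion (Section 2.3.2). Section 2.5 describes this delay as the period of greatest arrhythmia risk. A change-based event seen at the end of infusion or at 1 hour could precede the peak, and the literal stop rule would move that patient to hourly ECGs at once. Two sites following the same protocol could monitor the same tracing differently.

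**Working it through.** **1. The plan's own figures reproduce.** For TH-CR-601 (Section 2.3.2, 21 subjects):
- Grade 3 QTc prolongation: 10/21 = 47.6% (stated 48%).
- Change above 60 msec: 38% × 21 = 7.98, so 8 subjects; 8/21 = 38.1%.
- QTcF of at least 501 msec: 2/21 = 9.5% (stated 10%).
- 8 + 2 = 10, which implies that the two groups do not overlap. The change limb then accounts for 8 of 10.

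**2. One patient.** Pre-infusion 400 msec, post-infusion 470 msec.
- Rise = 470 − 400 = 70 > 60, so Grade 3 by Sections 6.7.1 and 8.5.
- 470 ≤ 480, so the stop rule of Section 6.9.2.1 is already met.
- Under the two-limb definition the patient stays Grade 3 until QTcF is at or below 400 + 60 = 460 msec.

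**3. Every patient in the row.** Entry requires QTcF ≤ 500. The stop bands (481 to 500, or ≤ 480) together cover every whole-msec value up to 500, so entry implies exit. Under the two-limb definition entry implies the opposite, because the rise is above 60.

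As a count, take pre-infusion values of 350 to 449 msec. The lower end is an assumption; the upper end is the pre-infusion limit in Section 6.5. For pre-infusion b, the qualifying post-infusion values run from b + 61 to 500, which is 440 − b values. There are none once b reaches 440. The sum is 90 + 89 + … + 1 = 90 × 91/2 = 4,095 pairs.

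| Reading of the stop rule | Pairs already meeting it at the trigger |
|---|---|
| Absolute bands only | 4,095 of 4,095 |
| Both limbs | 0 of 4,095 |

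This restates the definitions. It shows that the two readings give opposite answers, not how often the case occurs. For triggers at 501 msec or above, neither reading is met at the start.

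**4. Whether another section settles it.** None does.
- Table 7's Grade 2 row is a band of 481 to 500 msec with no exclusion for a large rise. A patient going from 420 to 490 msec (+70) fits both that row and the change-based Grade 3 row.
- Footnote 1 of the Schedule glosses Grade 3 as 501 msec or more only, while the dagger footnote uses both limbs.
- The copy of the dagger footnote in SAP Table 2 (footnote 2) has ≤ 499 msec where the protocol has ≤ 480. It also shows the 60 msec limb without a greater-than sign, which may be a text-extraction loss.

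**5. Size across both Phase 2 studies (Section 2.3.2).** 16 patients had a change above 60 msec and 10 had QTcF of at least 501 msec. The overlap lies between 0 and 10, so change-only patients number between 16 − 10 = 6 and 16. If the 19 Grade 3 events are exactly the union, the overlap is 10 + 16 − 19 = 7 and change-only is 9 of 19 (47%). That is an assumption: the stated 21% and 34% fit 47 patients (10/47 = 21.3%, 16/47 = 34.0%), whereas the adverse event counts use 51.

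**The case against.** The best defence is that the bracketed msec values merely label the bands. Grade 2 then means no longer Grade 3, a patient with a rise above 60 msec is not yet there, and the Table 7 row works as intended. A second defence runs the other way: the text after Table 7 says the guidance rests on absolute QTcF, a deliberate departure from the CTCAE.

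Both are reasonable, and they lead to opposite answers, so together they show that the text needs reconciling. The first asks the reader to add a limb that Section 6.9.2.1 leaves out of its end point. The second would leave the monitoring order in the change-based row with no effect, and the passage it relies on explains dose reduction, not ECG frequency.

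A reader might infer three stronger points. The documents do not support them.
- *That these patients may go home at once, so the Section 2.5 safeguard is void.* Discharge still needs two measurements at least 15 minutes apart after the 4-hour point, no significant arrhythmia, and assessment before leaving. ECGs also continue hourly. Only the QTcF part is already met, and only on the absolute reading; Table 7 and Section 2.5 give no msec value for it.
- *That recorded event durations will differ between sites.* Section 8.2.3 sets the end date of an adverse event separately, by full resolution or return to baseline. SAP Sections 14.1 and 14.4 plan no summary of QTc event duration.
- *That about 80% of Grade 3 QTc events are affected in general.* That share comes from one study of 21 subjects; the pooled data allow a wide range.

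**Conclusion.** The inconsistency is real and concerns the wording of a safety-monitoring rule. Read literally, Section 6.9.2.1 and the Schedule footnote end close monitoring at the triggering ECG for every event in Table 7's change-based row; by the two-limb Grade 3 definition, none of those events has resolved. For discharge there is an ambiguity about the QTcF component, not an empty safeguard.

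The affected group is not small: 8 of 10 Grade 3 QTc subjects in TH-CR-601, if the limbs are disjoint and those 8 stayed at or below 500 msec, and 6 to 16 patients across both studies. Those figures measure change from baseline, whereas this protocol uses change from pre-infusion, so they indicate scale only. The point should be corrected; it does not touch the response-rate design or its error rates.

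**What to change.** Reconcile protocol Sections 2.5, 6.7.1 (the Grade 3 definition, Table 7 and the text after it), 6.9.2.1 and 8.5 with the Schedule of Events footnotes, and align the footnote in SAP Table 2. Each should state the same thing: whether resolution to Grade 2 or lower, first for ending the 15 to 30 minute ECGs and then for discharge, is judged on absolute QTcF only or on both limbs of the Grade 3 definition. In the same pass, align Section 8.5, which writes the change limb once as > 60 and once as ≥ 60 msec. The clinical choice is the sponsor's.

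The cost is a few words in several places, with no effect on sample size or analysis. If both limbs are chosen, some patients would have more ECGs of a kind already in the protocol. SAP Section 4 reports that the trial was discontinued early, so the correction matters for any reuse of this text and for stating in the study report which reading sites applied.
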